### Plausibility of proportional hazards assumption

The plausibility of the proportional hazards assumption will be assessed by visually examining both the plot of the log of the negative log of Kaplan-Meier estimates of the survival function versus the log time for evidence of non-parallelism and the smoothed plot of the scaled Schoenfeld residuals to directly visualize the log hazard ratio (Grambsch and Therneau, 1994), for each stratum separately, and by including a time-treatment interaction term in the Cox model (time log transformed). The significance of the interaction will be tested at the 5% type I error level. If the interaction is significant and there is strong evidence of non-proportionality from the plots, time-dependent hazard ratios will be estimated with the model that includes the interaction term.

### Interaction between pantoprazole and antithrombotic treatment groups

The randomized antithrombotic treatment was to be stopped with the Final rivaroxaban/aspirin Follow-up Visit. Hence, the analysis of joint effects and interaction between antithrombotic and pantoprazole treatments on the pantoprazole outcome as described below will be based on the rivaroxaban/aspirin follow-up data scope, including events from randomization up until Final rivaroxaban/aspirin Follow-up Visit.

The joint effect and interaction between the antithrombotic and pantoprazole study groups on the pantoprazole outcome will be explored based on the intention-to-treat principle in subjects randomized to receive pantoprazole 40 mg od or pantoprazole placebo. The analysis will use two separate Cox proportional hazards models, one for the comparison of rivaroxaban 2.5 mg bid + aspirin 100 mg od vs. rivaroxaban placebo + aspirin 100 mg od, and one for the

comparison of rivaroxaban 5 mg bid+ aspirin placebo vs. rivaroxaban placebo + aspirin 100 mg od. The models will include:

- a covariate for the effect of the considered rivaroxaban-based treatment group vs. the aspirin-control group,
- a covariate for the effect of pantoprazole 40 mg od treatment group vs. pantoprazole placebo-control group,
- an interaction term of these two factors.

Therefore, the Cox proportional hazards model (e.g., for the comparison of rivaroxaban 2.5 mg bid + aspirin 100 mg od vs. rivaroxaban placebo + aspirin 100 mg od) can be described by the following equation:

$$h(t, x_{1i}, x_{2i}) = h_0(t) \exp(\beta_1 x_{1i} + \beta_2 x_{2i} + \beta_{12} x_{1i} x_{2i}),$$

where

$h(\cdot)$  hazard function for pantoprazole outcome as a function of time and subject's covariates

$h_0(\cdot)$  unspecified underlying baseline hazard function for pantoprazole outcome

$t$  time (in days) relative to the randomization date

$x_{1i}$  antithrombotic treatment group of subject  $i$   
(0 corresponds to "rivaroxaban placebo + aspirin 100 mg od (control)" and 1 corresponds to "rivaroxaban 2.5 mg bid + aspirin 100 mg od")

$x_{2i}$  pantoprazole group of subject  $i$   
(0 corresponds to "pantoprazole placebo-control group" and 1 corresponds to "pantoprazole 40 mg od treatment group")

$\beta_1, \beta_2, \beta_{12}$  unknown parameters (to be estimated)

SAS program code corresponding to the following will be used:

```
PROC PHREG DATA = <dataset>;
  MODEL ttevalue * ttecnsr(0) = trtgrp pn ppilgrp n trtgrp*n ppilgrp n /
    RL TIES=EFRON ALPHA=0.05;
RUN;

/*
where
dataset = name of sub-dataset including all ITT subjects randomized to
          respective rivaroxaban treatment group and control group
trtgrp n = variable coding randomized antithrombotic treatment group
          (0 = control group, 1 = rivaroxaban 2.5 mg + aspirin 100 mg)
ppilgrp n = variable coding randomized pantoprazole treatment group
          (0 = pantoprazole placebo, 1 = pantoprazole 40 mg treatment)
ttevalue = time to first occurrence of pantoprazole outcome event
ttecnsr = censoring index (0 = right-censored, 1 = event)
*/
```

## Additional analyses

Additional exploratory analyses will include, e.g., a comparison of subjects of the ITT analysis set who were not randomized to receive pantoprazole 40 mg od or pantoprazole placebo with subjects randomized to pantoprazole placebo with regard to the pantoprazole outcome during the Rivaroxaban/aspirin follow-up data scope.

### 5.2.4 Further Statistical Analysis for the Pantoprazole Randomization

Furthermore, the following additional statistical analyses will be provided:

- For the components of the unrefuted GI outcome, descriptive statistics and Kaplan-Meier estimates will be provided and the components will be analyzed using the stratified log-rank test and the Cox proportional hazards model as described above in the pantoprazole ITT analysis set for the ITT data scope for CDB2.
- For the unrefuted GI outcome and its components, descriptive statistics will be provided and an analysis using the stratified log-rank test and the Cox proportional hazards model as described above will be repeated in the pantoprazole safety set for the pantoprazole treatment emergent data scope.

### 5.2.5 Subgroup Analyses

Subgroup analyses for comparison of pantoprazole 40 mg and pantoprazole placebo will be performed based on the pantoprazole ITT analysis set for the ITT data scope for CDB2.

Homogeneity of treatment effect (i.e., the effect of pantoprazole study treatment on the pantoprazole outcome) will be examined for the following subgroup variables, where important subgroups are distinguished from “other” subgroups that are examined to assess the consistency of a treatment effect:

#### Important subgroups

- Antithrombotic treatment group (rivaroxaban 2.5mg, rivaroxaban 5mg, aspirin 100mg)
- Coronary artery disease (yes, no)
- Peripheral artery disease (yes, no)

#### Other subgroups

- Region
  - North America, Western Europe and AUS/ISR/ZAF, Eastern Europe, Asia Pacific, and South America, see SAP, version 4.1, Appendix 10.1
  - US, non-US
- Sex (male, female)
- Age
  - Categories 1: <55, 55 to <65, 65 to 75, >75 years
  - Categories 2: < 65, ≥ 65 to < 75, ≥ 75 years
- Race (White or Caucasian, Black or African American, Asian, other)
- Body weight at baseline (≤ 60 kg, > 60 kg)
- Baseline renal function
  - estimated glomerular filtration rate (eGFR) categories 1: <60, ≥60 mL/min

- eGFR categories 2: < 15, 15 to < 30, 30 to < 60,  $\geq$  60 mL/min
- eGFR categories 3: < 30, 30 to 50, >50 to 80 ml/min, >80 ml/min
- Smoking status
  - Tobacco use at baseline (yes, no)
  - History of tobacco use (yes, no)
- Baseline diabetes (yes, no)
- History of peptic ulcer (yes, no)
- History of Helicobacter pylori (yes, no, unknown)
- Baseline NSAID use (yes, no)

Additional subgroup analyses, if identified, can be specified. The pre-specified categories may be collapsed if the number of events is too small for some subgroups. In addition to analyses of the subgroups listed above, analyses for the Asian populations, especially Chinese and Japanese subjects, will be performed as required and presented in separate reports.

Homogeneity of study treatment effect in subgroups, both in magnitude and direction, will be assessed by adding a covariate for the subgroup variable and the corresponding treatment-subgroup interaction to the respective stratified Cox proportional hazards model used in the main analysis.

As the number of subgroup analyses may be large, the probability of observing at least one statistically significant but spurious interaction is high despite the lack of a biological or pharmacological basis for expecting an interaction. Thus any significant interactions in the analysis of primary outcomes will be interpreted as “flags” to prompt further investigation.

No interactions with any of the subgroup variables are expected. Furthermore, in the analysis of all outcomes, if the interaction term is significant at the 5% type I error level, the likelihood ratio test proposed by Gail and Simon (1985) will be performed to test the hypothesis that there is no crossover or qualitative interaction at the 1% type I error level ( $H_0$ : The direction of treatment effect is the same for all levels of a subgroup variable vs.  $H_1$ : The direction of treatment effect is different for at least one level of a subgroup variable). As was shown by Li et al (2007), the probability of observing the treatment effect in the opposite direction to the true overall treatment effect for at least one subgroup level is not negligible. The contributing factors may be small subgroup sizes, imbalance of randomized groups within the subgroups, and small true overall treatment effect.

Following the test of interaction, hazard ratios with 2-sided 95% confidence intervals for the treatment effect will be estimated separately within each level of a subgroup variable using the stratified Cox proportional hazards models that were used in the main analyses of study outcomes.

### **5.2.6 Potential Modification of Rivaroxaban Treatment Effect by Pantoprazole**

The results of the Cox proportional hazards model including the effects of antithrombotic treatment, pantoprazole treatment, and the interaction of those have been reported for selected outcomes based on CDB1 to exclude an interaction effect between antithrombotic and pantoprazole treatment.

To further investigate if pantoprazole treatment has the potential to modify the rivaroxaban treatment effect on the following unrefuted outcomes

- Primary efficacy outcome
- Composite of MI, ischemic stroke, and CV death
- Secondary efficacy outcome
- Modified ISTH major bleeding
- Modified ISTH major bleeding in gastrointestinal tract
- GI bleeding (composite of the first three components of the GI outcome referring to upper GI bleeding),

these outcomes will be evaluated for the ITT analysis set by antithrombotic treatment groups in the rivaroxaban/aspirin follow-up data scope by depicting

- the number of subjects with event, crude incidences, incidence rates and Kaplan-Meier estimates in
  - the ITT analysis set
  - the pantoprazole treatment groups
    - pantoprazole 40mg od
    - pantoprazole placebo od
    - not randomized to pantoprazole/placebo
- the assessment of homogeneity of rivaroxaban treatment effect by the pantoprazole treatment groups (including subgroup-interaction p-value)
- forest plots for the above.

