### Analysis of the joint effect and/or interaction of study treatments

In addition, an analysis of the joint effect and/or interaction between rivaroxaban-based anti-thrombotic therapy and proton pump inhibitor use on the primary efficacy outcome will be performed for those subjects randomized to both antithrombotic and pantoprazole study medication. Joint effect and interaction between the antithrombotic and pantoprazole study groups on the primary efficacy outcome will be explored based on the intention-to-treat principle. The analysis will use two separate Cox proportional hazards models, one for the comparison of rivaroxaban 2.5 mg bid + aspirin 100 mg od vs. rivaroxaban placebo + aspirin 100 mg od, and one for the comparison of rivaroxaban 5 mg bid+ aspirin placebo vs. rivaroxaban placebo + aspirin 100 mg od.

The Cox proportional hazards model (e.g., for the comparison of rivaroxaban 2.5 mg bid + aspirin 100 mg od vs. rivaroxaban placebo + aspirin 100 mg od) can be described by the following equation:

$$h(t, x_{1i}, x_{2i}, x_{3i}) = h_0(t) \exp(\beta_1 x_{1i} + \beta_2 x_{2i} + \beta_{12} x_{1i} x_{2i}),$$

where

$h(\cdot)$  hazard function for primary efficacy outcome as a function of time and subject's covariates

$h_0(\cdot)$  unspecified underlying baseline hazard function for primary efficacy outcome

$t$  time (in days) relative to the randomization date

$x_{1i}$  antithrombotic treatment group of subject  $i$   
(0 corresponds to "rivaroxaban placebo + aspirin 100 mg od (control)" and 1 corresponds to "rivaroxaban 2.5 mg bid + aspirin 100 mg od")

$x_{2i}$  indicator variable for "pantoprazole 40 mg od treatment group",  
i.e.,  $x_{2i} = 1$  if subject  $i$  was randomized to pantoprazole 40 mg treatment,  
 $x_{2i} = 0$  if subject  $i$  was randomized to pantoprazole placebo

$\beta_1, \beta_2, \beta_{12}$  unknown parameters (to be estimated)

SAS program code corresponding to the following will be used:

 Text added as per modification 7 in integrated SAP, Version 3.0.

```
PROC PHREG DATA = <dataset>;
  MODEL ttevalue * ttecnsr(0) = trtgrp pn ppigrpn trtgrp*ppigrpn
    / RL TIES=EFRON ALPHA=0.05;
RUN;

/*
where
dataset = name of sub-dataset including all ITT subjects randomized to
          respective rivaroxaban treatment group and control group
trtgrp  = variable coding randomized antithrombotic treatment group
          (0 = control group, 1 = rivaroxaban 2.5 mg + aspirin 100 mg)

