## 2. Study Objectives

The main objective for the pantoprazole randomization is

- To determine whether pantoprazole 40 mg od compared with placebo reduces the risk of upper gastrointestinal bleeding, ulceration, or gastrointestinal obstruction or perforation in subjects with CAD or PAD receiving antithrombotic medications.

Other objectives for the pantoprazole randomization are:

- To determine the effect of pantoprazole 40 mg od compared with placebo on the risk of pneumonia, clostridium difficile (C. diff) and other enteric infections, bone fractures, and new diagnosis since randomization of gastric atrophy, chronic kidney disease, diabetes, chronic obstructive lung disease and dementia in subjects with CAD or PAD.
- To determine whether treatment with pantoprazole 40 mg od potentially modifies the effects of antithrombotic treatment on major cardiovascular outcomes or bleeding events. I.e. whether pantoprazole interacts with the treatment effects of rivaroxaban 2.5 mg bid/aspirin 100 mg od vs. aspirin 100 mg od in its impact on outcomes.
- To determine whether treatment with pantoprazole 40 mg od has an effect on premature discontinuation of antithrombotic study treatment.

For further details on study objectives, please refer to integrated [SAP](#), version 4.1.

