### 4.1 Analysis Sets

The following analysis sets will be used for the analysis of the data from CDB2.

- **Intention-to-treat Analysis Set (ITT):**  
The intention-to-treat analysis set, also termed full analysis set in the International Conference on Harmonization (ICH) E9 guideline, includes all subjects randomized to antithrombotic study treatment. The ITT set comprises both subjects randomized to pantoprazole/placebo and subjects not randomized to pantoprazole/placebo.
- **Pantoprazole ITT Analysis Set (pantoprazole ITT):**  
The pantoprazole ITT analysis set comprises all subjects that have been randomized to pantoprazole 40mg or pantoprazole placebo.
- **Pantoprazole Safety Analysis Set (pantoprazole SAF):**  
The safety analysis set for secondary analyses related to the pantoprazole randomization (pantoprazole safety analysis set) will include all subjects randomized to pantoprazole/placebo who received at least one dose of randomized pantoprazole/placebo medication.  
A subject is considered to have taken at least one dose of pantoprazole/placebo study

medication if the date of permanent discontinuation of pantoprazole/placebo study treatment is later than the randomization date.

[figure not shown]

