## 5. Statistical Methodology

All data will be listed and all variables will be summarized by means of descriptive statistics according to their type.

Summaries by randomized study treatment pantoprazole and pantoprazole placebo using appropriate descriptive statistics will be provided overall and/or by antithrombotic treatment group for all study variables including demographic and baseline characteristics. The group not randomized to pantoprazole/placebo due to continuous need for a PPI will be presented separately. No imputation will be applied. Descriptive statistics such as mean, standard deviation, median, quartiles, minimum, and maximum will be used to summarize continuous variables. Counts and percentages will be used to summarize categorical variables. Life tables and Kaplan-Meier estimates will be used to summarize time-to-event variables. Graphical data displays may also be used to summarize the data. Confidence intervals will be provided at a 2-sided level of 95% unless otherwise stated.

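### In the PPI-specific SAP, section 5.2.6, the p-value for modification of the rivaroxaban effect by pantoprazole spans a third group never randomized to pantoprazole, so a significant result cannot be attributed to pantoprazole

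*SAP*

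**What the plan says.** Among the objectives in section 2 of the PPI-specific SAP is: "To determine whether treatment with pantoprazole 40 mg od potentially modifies the effects of antithrombotic treatment on major cardiovascular outcomes or bleeding events". Section 5.2.6 repeats the aim: "To further investigate if pantoprazole treatment has the potential to modify the rivaroxaban treatment effect on the following unrefuted outcomes". Six outcomes follow: the primary efficacy outcome; MI, ischemic stroke and CV death; the secondary efficacy outcome; modified ISTH major bleeding; the same in the gastrointestinal tract; and upper GI bleeding.

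The population is the full ITT set: "these outcomes will be evaluated for the ITT analysis set by antithrombotic treatment groups in the rivaroxaban/aspirin follow-up data scope". Section 4.1 defines it: "The ITT set comprises both subjects randomized to pantoprazole/placebo and subjects not randomized to pantoprazole/placebo". Under the label of pantoprazole treatment groups, 5.2.6 lists pantoprazole 40 mg, pantoprazole placebo, and not randomized to pantoprazole/placebo. The next item asks for "the assessment of homogeneity of rivaroxaban treatment effect by the pantoprazole treatment groups (including subgroup-interaction p-value"). No sentence limits that p-value to the two randomized arms, and no significance level or degrees of freedom are given.

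Section 5 of the same document gives the reason the third group exists: "The group not randomized to pantoprazole/placebo due to continuous need for a PPI will be presented separately".

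The integrated SAP 4.1, section 6.2.1.2, handles the same question for the primary efficacy outcome differently. There the interaction analysis "will be performed for those subjects randomized to both antithrombotic and pantoprazole study medication".

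**The concern.** The objective concerns the effect of a drug, and that drug was randomized in only two of the three levels. The third level was selected by a clinical need for a PPI. If the rivaroxaban HR differs there, the cause may be who those patients are, their open-label PPI, or chance. A three-level homogeneity test pools that difference with the randomized comparison into one p-value, placed under a title and aim that name pantoprazole.

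A significant result could therefore be read as pantoprazole changing the rivaroxaban effect when it changes nothing. The bleeding outcomes matter most, because a continuous need for a PPI is plausibly tied to gastrointestinal risk.

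**Working it through.** **Is the test three-level as written?** Section 5.2.6 names the ITT set, which includes the non-randomized subjects, lists three levels under the group label, and then uses that label to define the test. Section 5.2.7 uses the same label for two arms, but only after restricting to the pantoprazole ITT set; 5.2.6 makes no such restriction. Three levels, hence 2 df, is the plain reading.

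**Which randomized-only interaction tests exist?**
- Primary efficacy outcome: yes, in SAP 4.1 section 6.2.1.2.
- Selected outcomes at the first database release: yes according to 5.2.6, but they are not named.
- Upper GI bleeding: arguably. Section 5.2.3 applies its analyses to the variables of 5.2.1, which include this composite. Its randomized-only interaction model uses the rivaroxaban/aspirin follow-up scope, though it speaks of the pantoprazole outcome in the singular.
- The other 5.2.6 outcomes, notably modified ISTH major bleeding and GI major bleeding, in the rivaroxaban/aspirin follow-up scope: none specified.

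**Size of the problem.** The plan gives no power or error figure for this test, so there is none to reproduce. Inputs for an illustration on the primary efficacy outcome:
- Events: about 1,100 in three arms at the first interim analysis (SAP 4.1, section 4.4); two of three arms give 1,100 × 2/3 ≈ 733 per comparison.
- Share randomized to pantoprazole/placebo: 16,440/27,400 = 60%, or 16,440/21,400 = 77%. The count of 16,440 belongs to protocol version 2.0, whose total was 21,400; both splits are shown.
- Events are assumed proportional to subjects: 220, 220 and 293 at 60%; 282, 282 and 170 at 77%.
- Level 5%, as for the SAP 4.1 interaction model.
- Ratio r of the rivaroxaban HR in the third group to that in the other two: an assumption, so a range. SAP 4.1 treats 1.25 as the smallest clinically significant synergy.

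With Var(log HR) = 4/events per level and no pantoprazole effect, the 2-df test has non-centrality λ = (E/4) × f(1−f) × (ln r)², where E is the number of events and f the share randomized. At r = 1.25 and f = 0.60: λ = 183.3 × 0.24 × 0.0498 = 2.19. The non-central chi-square probability of exceeding 5.99 is then 24%.

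| r in the third group | Three-level test, 60% randomized | Three-level test, 77% randomized | Randomized 1-df test |
|---|---|---|---|
| 1.1 | 8% | 7% | 5% |
| 1.25 | 24% | 19% | 5% |
| 1.4 | 50% | 39% | 5% |
| 1.6 | 80% | 67% | 5% |

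**Power for a true modification.** Let pantoprazole change the rivaroxaban HR by a ratio of 1.5. The 1-df test has λ = (E × f/16) × (ln 1.5)² = 27.5 × 0.1644 = 4.52 at 60%, which gives 57% power. The three-level test has 46% if the third group lies midway between the randomized arms, and 61% if it matches one of them. At 77% randomized the figures are 67%, 57% and 66%. Power can move either way.

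**The case against.** The strongest reply is that 5.2.6 is a supplementary display, and much of it stands.

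- A reader might infer that the objective has no valid test. It does: a randomized-only interaction is planned for the primary outcome, was reported for selected outcomes, and arguably covers upper GI bleeding. SAP 4.1 also refers its secondary efficacy and primary safety analyses back to the methods of 6.2.1.2, which could carry the interaction model to modified ISTH major bleeding. That is by cross-reference only, and in the scope ending at the 6 February 2017 cut-off.
- The introduction of the PPI-specific SAP also asks, more broadly, whether PPI treatment interferes with rivaroxaban. The three levels are strata of the antithrombotic randomization, so consistency across them is a reasonable thing to examine. This justifies showing the third group, but not presenting the joint p-value as evidence on pantoprazole.
- A reader might see a contradiction with the instruction to present the third group separately. That instruction concerns descriptive summaries, and the reason given elsewhere in the plan is unequal observation time, which the 5.2.6 data scope largely removes.
- Results by group and forest plots would reveal a signal driven by the third group, 5.2.5 treats significant interactions in primary outcomes as flags, and no decision hangs on this p-value. This limits the harm, but a reader would still take the printed p-value as the answer.
- A reader might conclude that the three-level test necessarily loses power. It does not, as the working shows.

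**Conclusion.** The point holds in a limited form. As written, the 5.2.6 p-value mixes a non-randomized contrast into a test that is meant to address modification by pantoprazole, and a significant value could not be attributed to the drug. The hazard ratio within each level is not in doubt. The gap is real for outcomes without a specified randomized-only test in this scope, chiefly modified ISTH major bleeding and GI major bleeding.

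The rates of 7% to 80% against 5% rest on assumed differences in PPI users, on planned rather than observed event counts, and on events split in proportion to subjects. They apply to the primary efficacy outcome; the documents give no event counts for the bleeding outcomes. The loss of attribution does not depend on any of these figures. Because the analysis is exploratory and partly covered elsewhere, the change is worth making but does not threaten the trial's main conclusions.

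**What to change.** In section 5.2.6, state that the p-value for modification by pantoprazole comes from the pantoprazole ITT set: pantoprazole versus placebo, 1 df, separately for each rivaroxaban comparison, in the rivaroxaban/aspirin follow-up scope. Keep the not-randomized group in the tables and forest plots as a separate row outside that p-value. If a three-level p-value is retained for the broader PPI question in the introduction, label it a non-randomized consistency check.

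The cost is one or two sentences and a changed dataset filter. No new data are needed and no subject leaves the display.
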